## **5. STUDY POPULATION**

As per protocol.

The study population is defined as those children living in the study areas who are < 5 years old.

### **5.1. Total enrolled cohort**

The Total enrolled cohort will include all subjects enrolled in the study.

## 5.2. According-to-protocol

The **According-To-Protocol** (ATP) cohort will include all evaluable subjects (i.e. those meeting all eligibility criteria).

The elimination codes for the defined populations are listed in the table below:

Cohort	Elimination codes
Total Enrolled cohort	900* Invalid informed consent or fraudulent data
ATP cohort	
2010 Inclusion criteria
 
 
Subjects' parent(s)/ LAR(s) who, in the opinion of the investigator, can and will comply with the requirements of the protocol.
 
Written informed consent provided from either the parent(s) or LAR of the subject.
 
Subject living in the HDSS or equivalent surveillance system area.
 
For enrolment in the active surveillance: children must be < 18 months of age OR For enrolment in the enhanced hospitalisation surveillance: children must be < 5 years of age and hospitalised at any time during the study.
 
 
Exclusion criteria
 
 
Child in care
 

	
2501 Subjects recruited in the group active surveillance 5-17months first DTP:
 
 
Subjects without DTP or without DTP vaccine dates available eliminated
 
Subjects eliminated if ICF signed more than 10 days after 1st DTP
 
Subjects eliminated if ICF signed at first visit available or after
 
Subjects for whom the hospitalisation admission date is before 1st DTP and : 
 
If hospital discharge date is known then subjects with ICF signed more than 7 days after hospital discharge are eliminated.
 
If hospital discharge date is missing with ICF signed more than 7 days after hospital admission are eliminated.
 
 
 

	
2502 Subjects recruited in the group active surveillance 5-17months catch up:
 
 
Subjects eliminated if ICF signed after first available visit
 
Subjects for whom the hospitalisation admission date is before ICF and: 
 
If hospital discharge date is known then subjects with ICF signed more than 7 days after hospital discharge are eliminated.
 
If hospital discharge date is missing with ICF signed more than 7 days after hospital admission are eliminated.
 
 
 

	
2503 Subjects recruited in the group enhanced hospitalisation surveillance (EHS) :
 
 
Subjects eliminated if no hospitalisation recorded or without hospitalisation admission dates available
 
Subjects with ICF before hospitalisation date -1 day are eliminated
 
Subjects for whom the hospitalisation admission date is before ICF and: 
 
If hospital discharge date is known then subjects with ICF signed more than 7 days after hospital discharge are eliminated.
 
If hospital discharge date is missing with ICF signed more than 7 days after hospital admission are eliminated.
 
 
 

	
2504 Subjects recruited in the group active surveillance 6-12 weeks:
 
 
Subjects without DTP or without DTP vaccine dates available eliminated
 
Subjects eliminated if ICF signed more than 10 days after 1st DTP
 
Subjects eliminated if ICF signed after first visit available
 

\*This code should be allocated only in very special occasion for fraudulent subject (e.g. lab samples received by error).

## 6. STATISTICAL METHODS

SAS version 9.4 or above will be used for statistical analysis.

All analyses will be conducted on the ATP cohort, unless otherwise detailed. The analyses will be done also on the Total cohort only if there are more than 5% of eliminated subjects; except for the demography where all the tables will be performed for both cohorts.

Main descriptive statistics (i.e. demographic characteristics) will be computed by study group, gender, EPI vaccine, study site and overall. Moreover, descriptive analysis of safety endpoints (i.e. AESI, Other AEs, meningitis) will be computed for specific sub-populations such as children with haemoglobinopathy and HIV-positive children.

Categorical variables will be summarised by the frequency and the percentage of each category. 95% confidence intervals (CIs) might also be presented and will be described in TFLs part. The following statistics will be presented for continuous variables: number of non-missing observations, mean, standard deviation, median, range (minimum and maximum) and 25th and 75th percentiles where required.

### 6.1. Group definition

The following group names will be used for the statistical analyses:

Group order in tables	Group label in tables	Group definition for footnote
Study Site *		
1	PPD _KE_Kombewa	Kombewa (Kenya)
2	PPD _GH_Kintampo	Kintampo (Ghana)
3	PPD _GH_Navrongo	Navrongo (Ghana)
Gender		
1	Female	
2	Male	
3	UNK	Unknown
Surveillance		
1	AS	Active surveillance
2	EHS	Enhanced hospitalisation surveillance
Study group		
1	AS 6-12W	Active surveillance 6-12 weeks
2	AS 5-17M	Active surveillance 5-17 months
3	EHS	Enhanced hospitalisation surveillance
EPI Vaccination status (see section 6.8 for definition)		
1	DTP/HepB/Hib vaccinated	Subjects vaccinated with DTP/HepB/Hib vaccine
2	Unvaccinated	Subjects not vaccinated with DTP/HepB/Hib vaccine
HIV Status		
1	Positive	
2	Negative	

Group order in tables	Group label in tables	Group definition for footnote
Haemoglobinopathies		
1	Yes	
2	No	

Tables will, in general, be displayed by study group for descriptive tables and for analysis of safety endpoints. When it will not be the case, it will be explicitly mentioned.

\* The data from Burkina Faso sites (Nouna and Sapone) will be neither in the interim analysis nor in the final analysis. Final data from Burkina Faso (not cleaned) will be presented in the progress report.

## 6.2. Disposition of subjects

A study flow diagram will be generated to present the number of subjects included in the Total enrolled and ATP cohorts.

Enrolment in each study site will be tabulated by study group.

Subject disposition will be presented by study site, study group and overall by computing:

- Number of enrolled children
- Number (%) of non-eligible children regarding inclusion and exclusion criteria
- Number of ATP children
- Main results
  - Number of subjects with at least one AESI and number of AESI
  - Number of subjects with at least one AE leading to hospitalisation or death and number of AE leading to hospitalisation
  - Number of subjects with at least one meningitis case and number of meningitis cases
  - Number of subjects with at least one episodes of any malaria and number of malaria cases

## 6.3. Analysis of demographics and characteristics at study entry

Demographic characteristics (age at informed consent and age at first visit, gender and household configuration) will be summarised by descriptive statistics per study group and by site. This analysis will be performed on the Total enrolled cohort, as well as on the ATP cohort.

## 6.4. Signs and symptoms, and medical history

- For Active surveillance, signs and symptoms and *usual* malaria preventive measures will be tabulated by study group and overall for all visits pooled.
  - The denominator will be the total number of visits and the numerator will be the number of subjects with at least one symptom among the visits.

- For hospitalised children from AS and EHS, malaria preventive measures, risk factors and comorbidity factors will be described by study group and overall for all hospitalisations pooled only: the denominator will be the total number of hospitalisations and the numerator will be the number of subjects with at least one risk among the hospitalisations.

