- **5-17 months group, enrolled at first DTP:** Children identified at first administration of DTP/HepB/Hib vaccine (usually given at 6, 10 and 14 weeks of age), for whom the home visits will be scheduled from 6 months of age onwards (mimicking administration of RTS,S/AS01_E in the 5-17 months group). In case a child is first seen during hospitalisation, before first administration of DTP/HepB/Hib vaccine, and meeting the inclusion criteria for active surveillance, the child can be enrolled in active surveillance (5-17 months group, enrolled at first DTP) during hospitalisation and home visits will be scheduled from 6 months of age onwards.

CONFIDENTIAL

115055 (EPI-MALARIA-002 VS AME)
Protocol Amendment 7 Final

- **5-17 months group, catch-up:** Children aged 5 to <18 months, identified at first encounter with the study staff, for whom the home visits will be scheduled from the first encounter with the study staff onwards (mimicking administration of RTS,S/AS01_E in the 5-17 months group). In case a child aged 5 to <18 months is first seen during hospitalisation and meeting the inclusion criteria for active surveillance, the child can be enrolled in active surveillance (5-17 months group, catch-up) during hospitalisation and home visits will be scheduled after being discharged from the hospital.

Enrolled children will be followed up through home visits for a total period of 44 months (see [Figure 1](#) and Section 9.2.7.1) except for subjects enrolled from Burkina Faso sites for whom their participation in the study has been early terminated. This follow-up period corresponds to the follow-up period of the children enrolled in EPI-MAL-003 (i.e. 24 months after the 4th dose of RTS,S/AS01_E).

In addition to the home visits, in children enrolled in the active surveillance, all visits to health care facilities (primary health care and hospital level) for any diseases, signs and symptoms will be reported to the study staff up to the end of the active follow-up period for each individual child (see Section 9.4.2). Thereafter there will be continuous monitoring of hospitalisations only, up to study conclusion (i.e. study end or child reaches 5 years of age, whichever occurs first) ([Figure 1](#)).

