- If a child, who is first identified during hospitalization by study staff, is not eligible for enrolment in active surveillance but fulfills the eligibility criteria for enrolment in enhanced hospitalisation surveillance, enrolment in enhanced hospitalisation surveillance will be proposed.

Note: 'first identified during hospitalization by study staff' means 'not already enrolled in the study'.

CONFIDENTIAL

115055 (EPI-MALARIA-002 VS AME)
Protocol Amendment 7 Final

In case a subject enrolled in enhanced hospitalisation surveillance is returning to the study area having previously been declared as an emigrant (migration being defined as spending more than 3 months outside the study area) this subject will keep the same subject study number and continue the original follow-up.

Enrolment into the study, as documented by signed or witnessed and thumb printed ICF, will allow for the collection of data that were generated during the hospitalisation under the local standards of care. In case a subject is hospitalised more than once during the study duration, the subject will be enrolled only once and followed for all hospitalisations occurring throughout the study duration or until he/she reaches 5 years of age.

Hospitalisation is defined as spending at least one night at a health care facility, for a subject registered in the study area.

Some primary health care facilities have beds available for overnight monitoring; these stays are considered to be “hospitalisations” for protocol purposes. There may be a difference in the degree of severity of cases admitted in the hospital and those hospitalised at primary health care facilities as the latter may include children with non-severe disease who live too far to be sent home on the same day. On the other hand, hospitalisations in primary health care facilities may also include cases that under European conditions would normally be referred to the hospital, such as: parental refusal to refer the child to a hospital, difficulties of transport or local standard practice. This issue will be addressed by identifying the type of health care facility (either hospital or primary health care facility) in case of hospitalisation. The type of health care facility will be included as covariate in the analyses, where appropriate.

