Visit days: 6-12 weeks group ⁶ (identified at first administration of DTP/HepB/Hib vaccine)		1 wk (±3 days) after 1 st DTP/ HepB/ Hib dose	1 wk (±3 days) after 2 nd DTP/ HepB/ Hib dose	1 wk (±3 days) after 3 rd DTP/ HepB/ Hib dose	6 wks (±5 days) after 3 rd DTP/ HepB/ Hib dose	6 mths (±2 wks) after 3 rd DTP/ HepB/ Hib dose	18 mths (±2 wks) after 3 rd DTP/ HepB/ Hib dose	5 wks (±5 days) post V6	12 mths (±2 wks) post V6	24 mths (±2 wks) post V6	At 5 yrs of age or study end ⁷ (±2 wks)
Visit days: 5-17 mths group (identified at first administration of DTP/HepB/Hib vaccine)		At the age of 6 mths (> 5 mths to < 7 mths)	4 wks (±3 days) post V1	4 wks (±3 days) post V2	5 wks (±5 days) post V3	6 mths (±2 wks) post V3	18 mths (±2 wks) post V3	5 wks (±5 days) post V6	12 mths (±2 wks) post V6	24 mths (±2 wks) post V6	At 5 yrs of age or study end ⁷ (±2 wks)
Visit days: 5-17 mths group (catch-up, enrolled at 5 to <18 mths of age)		First contact with study staff or 1 wk later	4 wks (±3 days) post V1	4 wks (±3 days) post V2	5 wks (±5 days) post V3	6 mths (±2 wks) post V3	18 mths (±2 wks) post V3	5 wks (±5 days) post V6	12 mths (±2 wks) post V6	24 mths (±2 wks) post V6	At 5 yrs of age or study end ⁷ (±2 wks)
Time point (Month)		M0	M1	M2	M3.5	M8	M20	M21.5	M32	M44	
Record information about malaria control measures, health care seeking behaviour, drug use and exposure to environmental hazards		•	•	•	•	•	•	•	•	•	
Record any outpatient visits and hospitalisations at all health care facilities		•	•	•	•	•	•	•	•	•	
Conduct physical examination, including systematic measurement of body temperature		•	•	•	•	•	•	•	•	•	
Record any detected signs and symptoms (including AESI, other AE leading to hospitalisation or death, meningitis, malaria, abscess at injection site, foot positional deformations)		•	•	•	•	•	•	•	•	•	

CONFIDENTIAL

115055 (EPI-MALARIA-002 VS AME)
Protocol Amendment 7 Final

Epoch		1									
Type of contact	Enrolment	V1	V2	V3	V4	V5	V6	V7	V8	V9	V10
Visit days: 6-12 weeks group ⁶ (identified at first administration of DTP/HepB/Hib vaccine)		1 wk (±3 days) after 1 st DTP/ HepB/ Hib dose	1 wk (±3 days) after 2 nd DTP/ HepB/ Hib dose	1 wk (±3 days) after 3 rd DTP/ HepB/ Hib dose	6 wks (±5 days) after 3 rd DTP/ HepB/ Hib dose	6 mths (±2 wks) after 3 rd DTP/ HepB/ Hib dose	18 mths (±2 wks) after 3 rd DTP/ HepB/ Hib dose	5 wks (±5 days) post V6	12 mths (±2 wks) post V6	24 mths (±2 wks) post V6	At 5 yrs of age or study end ⁷ (±2 wks)

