## 9. CHANGES FROM PROTOCOL

- *Risk factors of other AE leading to hospitalisation or death will not be done by means of univariate and multivariable Poisson regressions as for AESI, meningitis and malaria.*

*Indeed, from a clinical point of view such models will not be relevant in the context of EPI-MAL-002. Those models will be done in the before-after comparison in EPI-MAL-003 study.*

*Descriptive analyses of risk factors will be done as planned.*

- *Aggregated variables recorded in EPI-MAL-005 study will be part of the analysis of EPI-MAL-003 study including comparison of EPI-MAL-002 and -003 data. Those aggregated variables will not be included as risk factors of malaria in EPI-MAL-002 study.*
- *Handling of missing data is not relevant in the context of EPI-MAL-002 study. Therefore, Section 9.7.8.1 of the protocol will not apply.*
- *Version 17 terminology of the statistical catalogue will be used for the final analysis leading to a minor impact: in the Study Report, “subject” will be replaced by “participant”. The adaptation is already done in the SAP/TFLs*

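### SAP 6.4 divides a count of children by a count of visits or hospitalisations, so its percentages describe neither children nor contacts

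*SAP*

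**What the plan says.** SAP Section 6.4 has two bullets.

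- **Active surveillance.** Signs and symptoms and usual "malaria preventive measures will be tabulated by study group and overall for all visits pooled". The rule beneath reads: "The denominator will be the total number of visits and the numerator will be the number of subjects with at least one symptom".
- **Hospitalised children from active and enhanced hospitalisation surveillance.** Malaria preventive measures, risk factors and comorbidity factors are described by study group and overall, with all hospitalisations pooled: "the denominator will be the total number of hospitalisations and the numerator will be the number of subjects with at least one risk".

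The opening of SAP Section 6 makes these ratios percentages: "Categorical variables will be summarised by the frequency and the percentage of each category".

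SAP Section 9 withdraws the regression models of risk factors for other adverse events leading to hospitalisation or death, and adds: "Descriptive analyses of risk factors will be done as planned".

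Elsewhere the SAP keeps the units apart. Section 6.9.3.1 reports the number and percentage of subjects with each endpoint, and separately the number of events and of associated visits or hospitalisations. I found nothing in the SAP text that corrects the rule in Section 6.4.

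**The concern.** A percentage needs one unit above and below the line. Here the numerator counts children and the denominator counts contacts, so the quotient is a proportion of neither. It falls as contacts accumulate even when the share of affected children stays the same. Two columns with the same share of affected children will differ if their mean contacts differ.

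The stake is descriptive but not empty. Describing risk factors for other adverse events leading to hospitalisation or death is a stated secondary objective. With the models withdrawn, only description remains for it, and the second bullet of Section 6.4 is the only descriptive tabulation of risk factors that I found in the SAP text. Section 9 does not cite Section 6.4, so the link is plausible but not stated. The first bullet would also describe malaria preventive measures in a population where, by Protocol Section 9.2, high bed-net coverage was one criterion for choosing the countries.

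**Working it through.** The documents give no figure for these tables, so there is none to reproduce. The check is algebra plus stated assumptions.

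**Inputs**

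- Home visits: Protocol Table 4 records signs and symptoms, and malaria control measures, at V1 to V9. The scheduled maximum is therefore 9 per child, over the period in "Enrolled children will be followed up through home visits for a total period of 44 months". The mean number attended is not given; I assume 5 to 9.
- Hospitalisations: under Protocol Section 9.2.1.1 a child hospitalised more than once is enrolled once and "followed for all hospitalisations occurring throughout the study duration or until he/she reaches 5 years of age". The mean per hospitalised child is at least 1 and otherwise not given; I assume 1.0 to 2.0.

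**Identity.** In one table column let S be the children with at least one positive contact, N the children with at least one contact, and V all contacts pooled. Then

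SAP figure = S/V = (S/N) ÷ (V/N),

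that is, the child-level percentage divided by mean contacts per child. It does not require equal contacts per child. A simulation of 20,000 children with 1, 3, 5 or 9 contacts each gave a child-level 35.2% and a SAP figure of 7.8%. The ratio was 4.506, equal to the simulated mean number of contacts.

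**Home visits, against a child-level target**

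| True share of children | Mean 5 visits | Mean 9 visits |
|---|---|---|
| 30% | 30/5 = 6.0% | 30/9 = 3.3% |
| 50% | 50/5 = 10.0% | 50/9 = 5.6% |
| 100% | 100/5 = 20.0% | 100/9 = 11.1% |

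Universal bed-net use would thus appear as 20.0% to 11.1%.

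**Home visits, against a visit-level target.** Suppose a sign is present at each visit with probability q, independently, over 9 visits. The SAP figure is [1 − (1 − q)^9]/9.

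| q (true visit-level) | SAP figure | Understated by a factor of |
|---|---|---|
| 1% | 0.96% | 1.04 |
| 10% | 6.8% | 1.47 |
| 50% | 11.1% | 4.51 |
| 90% | 11.1% | 8.10 |

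The error here is the number of positive visits per positive child: small for rare signs, large for anything that persists.

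**Hospitalisations, against a child-level target**

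| Assumed mean per child | A true 50% shows as |
|---|---|
| 1.0 | 50.0% |
| 1.1 | 45.5% |
| 1.2 | 41.7% |
| 1.5 | 33.3% |
| 2.0 | 25.0% |

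**Comparability between columns.** The divisor is specific to each column. The two active-surveillance groups share the V1 to V9 structure, but a child in the 6-12 weeks group who does not complete DTP misses V2 and/or V3 (Protocol Section 9.2.7.1). Children in enhanced hospitalisation surveillance leave when EPI-MAL-003 starts, whereas active-surveillance children who do not receive RTS,S continue (Protocol Section 9.2.7.1.12). The opportunity for repeat admission can therefore differ by column. The documents do not allow the difference to be sized.

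**The case against.** The case for leaving this alone has several parts.

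- *Pooling over visits suggests that a visit-level percentage was intended.* Possibly. For rare signs the figure would then be nearly right (0.96% against 1%). This limits the error for such signs, but not for preventive measures, and the sentence still needs correcting because its numerator counts subjects.
- *Nine visits is a ceiling.* This stands. Visits are abandoned after two failed attempts, and children leave through migration, death, reaching 5 years, study end or RTS,S vaccination. Hence the range of 5 to 9. The SAP does not say whether outpatient visits are pooled too; if they are, the divisor could exceed nine.
- *The rule names only a symptom, not a preventive measure.* True; applying it to preventive measures follows from its place under the bullet that covers both.
- *The reader can recover the child-level figure.* Partly. Frequencies are shown and enrolled numbers are reported by group, but the number of children with at least one visit or hospitalisation may need a separate count.
- *The mock tables may already use matched units.* They are a separate document that I could not check. If they do, they conflict with the SAP text, which should then be corrected.

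Two stronger readings are tempting. A reader might infer that every percentage under Section 6.4 is about nine times too low, and so that the risk-factor description is out by that factor. The documents do not support this: the home-visit table contains no risk factors, and the risk-factor table is divided by mean hospitalisations per child, which is not given and may be close to 1. A reader might also infer that groups with more contacts will look as if they carry fewer risk factors. That direction can follow from the algebra, but the documents give no contact counts by group to show that it will occur or how large it would be.

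**Conclusion.** Both bullets of SAP Section 6.4 are wrong as written. Each figure is the child-level percentage divided by mean contacts per child in its column, and should not be read as a proportion of children or of contacts, or compared between columns with different numbers of contacts.

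The size depends on the table. For home visits, a feature present in every child shows as 20.0% to 11.1% under the assumed mean of 5 to 9 attended visits. For hospitalisations, a true 50% shows as 50% to 25% under the assumed mean of 1.0 to 2.0; at a mean of exactly 1 there is no error.

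The consequence is confined to description. The co-primary incidence rates use person-time, or census person-years for children under 5. The Poisson risk-factor models take covariates from the first home visit or first hospitalisation (SAP Section 7.5.3.1). None of these draws on the Section 6.4 ratios. Nor would a corrected hospitalisation table by itself describe risk factors for other adverse events specifically, since it is specified by study group and overall, not by cause of admission.

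**What to change.** In both bullets of SAP Section 6.4, match the units:

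- Active surveillance: children with at least one report of the item, divided by children with at least one visit.
- Hospitalised children: children with at least one report of the factor, divided by children with at least one hospitalisation.

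Optionally add a second line giving contacts with the feature over all contacts. State whether outpatient visits are included, and name preventive measures explicitly in the numerator rule. Align the mock tables with the revised text.

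The cost is one denominator per table and a footnote. No new data are needed, and no other planned analysis changes.
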